## Overview

This is a validation study to evaluate the acceptability, feasibility and impact of CICADAS (Care Improving Cognition for ADolescents on the Autism Spectrum), a clinician-assisted, digital application that aims to prime the brain to engage in flexible, adaptive long-term learning about social-emotional events through closed-loop technology. The goal of this study is to evaluate the CICADAS app in adolescents with Autism Spectrum Disorder (ASD) and to prepare for a large-scale efficacy trial in this population.

## Specific Aims

This study will employ an innovative and evidence-based digital intervention that includes ten digital assessments (CICADAS app) that will capture data on sensory processing abnormalities and associated cognitive deficits. We will leverage pilot data collected in adolescents with Autism Spectrum Disorder (ASD) and accumulate preliminary evidence for CICADAS app to function as 1) a stand-alone treatment; 2) a primer for PEERS (Program for the Education and Enrichment of Relationship Skills); 3) an enhancer for PEERS. This study will test CICADAS app in adolescents with ASD in a three-arm, active-controlled, randomized crossover trial to document the acceptability and evaluate its potential as a stand-alone treatment, as a primer for PEERS, or as a treatment enhancer of PEERS.

## Background

Adolescence is a period of heightened, socio-affective, experience-dependent learning and neural plasticity, which manifests as increased regulation of emotional reactivity and greater social understanding—functions that are necessary to navigate a complex social world. During this period, neural networks underpinning affective information processing functionally mature, leading to adaptive changes in how adolescents experience and regulate emotions in response to social cues as well as how they understand the social world and others' mental states. However, for vulnerable populations, including adolescents with Autism Spectrum Disorder (ASD), exposure to complex interpersonal situations and peer networks can be challenging, and the avoidance of social interactions may preclude meaningful social experiences and impede social skills development.

The cognitive-behavioral therapy (CBT) based PEERS (Program for the Education and Enrichment of Relationship Skills) is one of few evidence-based treatments available that target social skills in adolescents with ASD. PEERS is a parent/caregiver-assisted, 16-week social skills intervention with 500+ certified providers across 70 countries and multiple Randomized Controlled Trials (RCTs) demonstrating its efficacy and effectiveness for adolescents. The program teaches how to solve real-life social dilemmas, appraise affect and social contexts, and initiate and maintain conversations while receiving feedback from peers

and clinicians. Additionally, structured practice interactions during socialization activities (e.g., playing sports, games, etc.) are integrated into the curricula. Concurrently, parents attend separate sessions and are taught to assist their teens by providing appropriate feedback as participants work on forming and maintaining friendships via weekly homework assignments. Notably, some adolescents benefit from PEERS more than others, implicating individual differences in response to treatment and highlighting the potential for developing treatment enhancers.

While myriad approaches have been attempted to remediate social functioning deficits in ASD, few have considered how sensory processing is a prerequisite for intervention success. Although Sensory Processing Abnormalities (SPA) have been noted since the earliest reports of ASD, historically, they had been considered secondary consequences of social cognitive processing impairments. Only in the most recent revision of the DSM was “hyper- or hypo-reactivity to sensory input or unusual interests in sensory aspects of the environment” added to the diagnostic checklist for ASD. However, recent estimates of sensory symptom prevalence in persons with ASD range from 69% to as high as 93%. Sensory processing difficulties correlate highly with levels of autistic traits in the general population, implicating SPA in social interaction difficulties. Further, prospective studies suggest that sensory difficulties might even precede and predict difficulties in social functioning. Sensory processing is crucial in the forming of reliable environmental percepts; perturbations in this process can have broad implications across different levels of cognitive functioning, impacting adaptive functioning across the lifespan. These sensory symptoms may originate from differences in low-level processing in sensory-dedicated regions in the brain, offering insight into circuit-level alterations in ASD. In fact, SPA are hypothesized to be an etiological and maintaining factor of social cognitive deficits in ASD, and are strongly associated with impaired community functioning, reduced capabilities for independent living, and reduced quality of life. These challenges in processing and integrating the elements of the dynamic social information into a stable representation are considered the underpinnings of social cognitive impairments, and might render the acquisition of social skills more problematic in ASD individuals with SPA. Thus, targeting SPA to enhance social skills intervention is warranted.

Although PEERS teaches adolescents to consciously alter their attention and behavior through instruction and practice, the program is unable to systematically target SPA and strengthen processing of basic sensory information. One promising approach to mitigate SPA may be through computerized Social Cognitive Training (SCT), which leverages repetitive implicit learning mechanisms to promote more adaptive processing styles for affective stimuli. One well-designed RCT has tested the combination of SCT and social skills training in adults with ASD and reported gains in cognitive abilities and functional outcomes. However, no studies

to date have investigated whether SCT can enhance response to social skills interventions in adolescents with ASD.

In recent years, multiple computerized SCT programs have been developed with the goal of improving social cognition in individuals with ASD (see *Table 1 for trials that included adolescents*). While data show promise overall, 30% of the participants did not show gains in social cognition beyond expected practice effects. In addition, some investigations in ASD reported improvement on the SCT exercises but no transfer of these gains to untrained cognitive outcome measures. Further, methodologies across SCT trials have been inconsistent—e.g., small sample sizes, single-arm or non-randomized controlled (NRS) designs, non-validated measures, lack of follow-up assessments, and permissive procedures. To address these limitations, we have integrated our team’s combined expertise in clinical care of youth with ASD, developmental neuroscience, and our considerable track-record in the development of digital platforms that provide assessment and treatment tools based on the principles of neuroplasticity, to identify three potential areas of innovation for SCT in ASD:

1) Existing SCT for adolescents with ASD target sensory processing using fixed repetitive parameters. This approach does not capitalize on the neuroplastic potential of circuits underlying information processing, and does not take advantage of the unique sensitive period of brain development that occurs in adolescence to maximally promote adaptive learning. Over the past three decades, research has documented the remodeling of distributed cortical and sub-cortical responses as an individual acquires new perceptual, cognitive, motor, or executive control abilities. This training induces selective positive physical changes in synaptic numbers and strengths that result in the “specialization” of neuronal patterns that support emergent behaviors. This synaptic-plasticity-generated specialization of cortical and sub-cortical networks represents the neural substrate of new training-induced learning. Neuroplasticity-based SCT (NB-SCT) is designed to drive stimulus-specific cell assemblies to represent all parametric aspects of behaviorally relevant inputs or actions in increasingly robust, discriminative, and more-salient forms. For example, a rich body of work has shown neuroplasticity-driven behavioral changes leading to gains in cognitive operations including: perceptual abilities; cortical sampling rates and integration times; processing speed; representations of the spatiotemporal and spectrotemporal features of complex acoustic, visual, and tactile stimuli. Additionally, a small number of neuroimaging studies have examined neural effects of SCT interventions in ASD and have reported neuroplasticity that results in activity/functional connectivity more similar to that of typically developing controls. For example, Bolte and colleagues demonstrated that facial affect recognition training in youth with ASD led to an increase in amygdala and fusiform gyrus activation post-training that correlated with cognitive improvements. Hence, we designed a suite of training exercises (see *Innovation*) that targets ASD-related SPA.

2) Existing SCT for ASD is non-personalized and does not take into account cognitive endophenotypes. Prior trials of computerized cognitive training in ASD have been implemented without knowledge of individual variation in brain function domains that may influence therapeutic response. This “one-size-fits-all” approach to SCT is problematic, as treatment failure occurs often which incurs substantial cost to the patient, family, and social system. To bend the curve on the individual outcomes of ASD and maximize response to SCT, it is necessary to characterize sensory processing in each individual participant and use this information to set targets and tailor the exercises accordingly. Thanks to data collected from 200+ adolescents without psychiatric illnesses, we can rely on brief assessments (*see Innovation*) that identify and monitor SPA at a subject-specific level, and propose personalized training exercises that target individual needs.

3) SCT is only available in specialized treatment centers. SCT programs often have a high scheduling burden, requiring multiple weeks of participation and regular in-person clinic visits. This time commitment can be untenable for caregivers who are employed, have other responsibilities to manage, or are without transportation. Additionally, for those who do seek treatment, barriers to receiving it include geographic location, availability of trained therapists, long waiting lists, and the requirement to take time off from school for clinic visits. The remote delivery of SCT through digital devices enables scheduling flexibility and decreases time burden, thus improving accessibility and compliance with intervention requirements, resulting in an increase in cost-effectiveness. In short, digital technology can facilitate access to, and engagement with SCT. In an effort to address these issues and improve outcomes, we propose CICADAS (Care Improving Cognition for ADolescents on the Autism Spectrum)—a digital application that provides an assessment of SPA to tailor the delivery of adaptive, individualized NB-SCT exercises for ASD. By systematically targeting SPA and social cognition deficits, CICADAS app is designed to prime the brain to learn cognitive and relational strategies taught during PEERS groups. We hypothesize that the delivery of the CICADAS app will maximize the impact of PEERS, promoting the generalization of learned skills in the natural environment, and ultimately improving real-world social functioning.

### **Pilot Trial Design and Procedures**

Participants will be recruited to join a pilot trial prior to the implementation of the three-arm, randomized crossover trial to assess feasibility and initial efficacy of CICADAS app in adolescents with ASD. During the pilot trial, three focus groups will be organized with a group of three adolescents with ASD and two PEERS clinicians to refine CICADAS app, qualitatively evaluate its manageability, clinical usefulness and acceptability, and ensure that the user experience and interface are sufficiently engaging to motivate sustained program use. After the focus groups are completed, participants will be granted access to CICADAS app for two weeks to test its features and evaluate its usability. At the end of the 2-week trial period, participants will offer feedback on the app through a 1:1 user interview with a member of the

research team. It is expected that participants will be enrolled in the pilot trial for approximately 4 weeks.

Participants must be between the age of 11 to 18 (inclusive) and have a clinical diagnosis of ASD. Participants must have access to reliable Internet connection and must be willing to engage in remote and/or in-person activities to qualify for enrollment.

Prior to initiating any pilot trial procedures, study personnel will screen potential participants (either over the phone or in-person) using an IRB-approved screening questionnaire that assesses for inclusion and exclusion criteria. If the potential participant appears eligible, they and their parents/legal guardian(s), when appropriate, will be invited to a consent/assent discussion with a designated team member prior to enrollment. Consenting/assenting to research activities will take place remotely or in a private room at the study site. During the consent/assent discussion, the qualified site study personnel authorized by the Site Principal Investigator (Site PI) and the potential participant and their parent/legal guardian will discuss the nature, purpose, and procedures of the pilot trial, the possible risks and benefits of participation, confidentiality, and the voluntary nature of participation in the pilot trial (emphasizing the participant's right to withdraw from the focus group at any time). Participants will also be informed of the compensation procedures; specifically, participants will be paid \$10 for completing the consent and screening procedures, \$25 for participating in each focus group session, \$25 for completing 2-weeks of CICADAS app activities, and \$15 for completing a 1:1 user interview. Participants that complete all activities will earn a total of \$125. Compensation will be provided through CashPass, a reloadable debit card through a third-party vendor, CT Payer. Payment will be provided upon exiting from the pilot trial, following the completion of the 1:1 user interview. If a participant leaves early, for any reason, and does not complete all focus group activities, they will be paid only for activities they have completed. After potential participants have agreed to participate in the pilot trial and completed informed consent/assent procedures, study personnel will confirm eligibility via clinical/medical history and assessments as needed.

Once three participants are deemed eligible and enrolled in the pilot trial, they will be scheduled for three focus group sessions that could occur in-person or remotely, to be completed over the course of approximately 2-weeks. Each session will last approximately 1 hour and will be facilitated by PEERS clinicians. After feedback from the focus group sessions is implemented into the app and dashboard design, the three adolescents will be granted access to the CICADAS app and engage in a 2-week trial period. This trial period will ensure that CICADAS app assessment data adequately orient the delivery of individualized neuroplasticity-based social cognitive training (NB-SCT) exercises. At the end of the 2-week trial period of CICADAS app, participants will be asked to rate their enjoyment, ease of use,

product quality, and perceived usefulness in a 1:1 user interview. Finally, we will submit these data from the trial period to our consultant to confirm that CICADAS app is suitable for the feasibility trial.

## General Study Design

We will employ a three-arm, active-controlled, randomized crossover trial to assess the safety and efficacy of CICADAS app in adolescents with ASD, and to evaluate its potential as a stand-alone treatment, as a primer for PEERS, or as a treatment enhancer of PEERS. We will randomize adolescents with ASD (ages 11-18) to CICADAS only, PEERS + CICADAS app, or PEERS + Active Control app.

Approximately 56 participants will be consented to ensure the successful completion of 48 participants (16 participants per treatment arm). A diagnostic interview will be performed to determine eligibility. Following inclusion and enrollment, participants will complete a set of assessments prior to the intervention to establish their baseline performance. Participants will then be randomized to the CICADAS only group (Arm A), PEERS + CICADAS app group (Arm B), or PEERS + Active Control app group (Arm C) and spend up to 16 weeks engaged in their assigned intervention. After 16 weeks, a full battery of assessments will be administered. For the next 16 weeks, Arm A will continue with PEERS only and Arms B and C will receive no treatment during this period. At the end of the intervention period, a full battery of assessments will be administered a second time to evaluate changes in performance. Finally, participants will be asked to fill out an online exit survey to rate enjoyment, usability, perceived benefits, and ease of fit into schedule.

During the first intervention period, participants assigned to the CICADAS only will complete NB-SCT exercises for 16 weeks. Participants assigned to PEERS + CICADAS will engage with the CICADAS app and complete weekly 1-hour PEERS group sessions for 16 weeks. Participants assigned to receive the PEERS + Active Control will engage in the Active Control app and complete weekly 1-hour PEERS group sessions for 16 weeks. During the second intervention period, participants assigned to receive PEERS only will complete weekly 1-hour PEERS group sessions for 16 weeks. During both intervention periods, these participants may have weekly electronic check-ins with site study personnel (as needed). The CICADAS app and the Active Control app icons, design and user experience will look the same as to not unblind the participants.

Each PEERS group session will consist of a minimum cohort of 3 participants and will meet as a group during the 16 week period. The PEERS clinician will meet with each participant individually for a brief introduction and orientation. The PEERS group sessions will be made available to meet in person or remotely. For remote PEERS group sessions, the study

coordinator and/or PEERS Clinician will create a virtual room open only to cohort participants, explain their role, and make introductions. Next, the PEERS clinician will invite participants to attend weekly 1-hour PEERS group sessions.

The protocol will be conducted in accordance with the protocol submitted to and approved by the reviewing Institutional Review Board and approval will be obtained prior to implementation.

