## **Inclusion/Exclusion Criteria**

Following informed consent, participants will be screened for the following inclusion/exclusion criteria.

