## Sample Size Justification

Attrition rates from the ASD pilot study conducted at University of Minnesota were > 30%. This high dropout rate can be ascribed to design issues, in that: (1) the sample recruited for the pilot consisted of adolescents who were not intrinsically interested in long-term treatment options for ASD, unlike the current target (adolescents already seeking PEERS); and (2) study coordinators had not been formally trained on how to keep participants engaged in a remote cognitive training intervention. By recruiting adolescents already seeking PEERS and by rigorously training our staff, we expect retention rate for this project to be in line with those of 1) cognitive interventions delivered to adolescents with ASD; 2) PEERS groups. We project a 15% non-completion rate estimate for this study. We will recruit 56 participants to obtain 48 study completers. As the primary aim of this study is to gather information about the feasibility, acceptability and usability of this approach, the sample size of N=56 is set primarily for practical reasons and not driven by hypothesis testing. This size will, however, provide data to power a subsequent pivotal efficacy trial in Phase II, and will provide the field validation data required to submit CICADAS to the FDA as a medical device for such a trial

under the 510k de novo process. We are confident that we will meet our recruitment goals with these resources in place.

Of interest to the design of our proposed trial, despite randomization to the auditory or visual training conditions, 73.2% of participants who were assigned to the Visual condition at BL completed the training whereas only 38.5% of participants who were assigned the Auditory Condition completed the program. This highlights the importance of personalized intervention programs that take individual differences (e.g., auditory sensitivity) into consideration. In fact, several participants who chose to discontinue attributed their decision to an aversion to the auditory stimuli used in the computer programs. Baseline SCAN Competing Words Test scores were significantly related to whether individuals randomized to the Auditory or Visual NB-SCT Modules completed their training [ $F(2,23) = 6.331, p = .006$ ]. In other words, participants randomized to the Auditory NB-SCT who did not complete their program had significantly more auditory processing difficulties than those who completed the program.

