### Statistical Plan

Traditional Randomized Control Trials may not be the most effective way to test the efficacy of deeply-tailored, adaptive interventions. Instead, well-conducted, properly powered clinical trials that incorporate crossover design may be more useful in investigating how to optimize/enhance an evidence-based treatment (PEERS) with the experimental adjunct/primer (CICADAS). **Our trial defines: (1) three first stage treatment options; (2) a mid-study assessment point, (3) three second stage treatment options.**

After screening and enrollment, participants complete the full battery of assessments at baseline (Week 0). At Stage 1, **48** adolescents will be randomized to a 16 weeks of CICADAS only (Arm A) vs 16 weeks of PEERS + CICADAS (Arm B) vs 16 weeks of PEERS + Active Control. In order to reduce variance, we will employ a Stratified Permuted Block Randomization Design with strata defined by sensory processing symptoms to balance the number of individuals with SPA across each trial arm. After 16 weeks, the full battery of assessments will be administered again. Arms A, B and C will receive no contact for 16 weeks. At the end of the intervention, the full battery of assessments will be administered for a third time.

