With 48 participants fully evaluated, we will not have enough power to detect a treatment augmentation effect ascribable to CICADAS. However, data from this pilot trial will be used to power a pivotal RCT in Phase II, as they will allow to explore whether:

- a) the concurrent delivery of CICADAS and PEERS for 16 weeks (B1-B2) induces greater improvements sensory processing, cognition, symptom reduction, social skills and behaviors, as well as quality of life, compared to CICADAS only (A1-A2) or PEERS + Active Control (C1-C2) – *preliminary efficacy of CICADAS as a treatment enhancer for PEERS*;
- b) The concurrent delivery of CICADAS and PEERS for 16 weeks (B1-B2) induces greater improvements sensory processing, cognition, symptom reduction, social skills and behaviors, as well as quality of life, compared to the sequential delivery of CICADAS and PEERS (A1-A3) – *preliminary testing of CICADAS as enhancer vs primer*;
- c) improvements sensory processing, cognition, symptom reduction, social skills and behaviors, and quality of life induced by the concurrent delivery of CICADAS and PEERS (B1-B2) are sustained after 16 weeks of no contact (B2-B3) – *durability of augmentation effects*.

To verify these experimental hypotheses, we will conduct the analysis based on the pre-intervention (baseline) and post-intervention data. The criterion for statistical significance is  $p < 0.05$ . Results with  $p < 0.1$  will be described as trends.

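### The SAP gives 48 as both the number randomised and the number fully evaluated, which allows no loss; at the protocol's 15% non-completion, 48 randomised gives about 41 completers.

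*Protocol*

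**What the plan says.** The number 48 is attached to different stages of the trial.

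- **Protocol, General Study Design:** 48 is the number finishing. "Approximately 56 participants will be consented to ensure the successful completion of 48 participants (16 participants per treatment arm").
- **Protocol, Sample Size Justification:** "We project a 15% non-completion rate estimate for this study", followed by "We will recruit 56 participants to obtain 48 study completers". The section adds that "the sample size of N=56 is set primarily for practical reasons and not driven by hypothesis testing".
- **Protocol, Inclusion/Exclusion Criteria:** "Following informed consent, participants will be screened for the following inclusion/exclusion criteria". Consent therefore precedes formal eligibility assessment, and Study Procedures places randomisation later still, after the baseline visit.
- **SAP, Statistical Plan:** at Stage 1, "48 adolescents will be randomized" to the three arms.
- **SAP, preliminary-efficacy text (after Primary Outcome - Feasibility):** the power remark starts from "With 48 participants fully evaluated".

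The protocol gives no number randomised. Neither document gives a screen-failure rate or says whether the 15% runs from consent or from randomisation.

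**The concern.** If 48 are randomised and 48 are fully evaluated, nobody is lost between randomisation and week 32. That conflicts with the protocol's 15%, and also with the SAP itself. The SAP separates the ITT set from a fully-evaluable set and a completer set, allows for participants who withdraw after randomisation and before treatment, and plans maximum-likelihood handling of missing data. The protocol's Withdrawal section likewise anticipates withdrawals because of the time the intervention takes.

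What is at stake is mainly when enrolment stops. A team working from the SAP would stop at 48 randomised. A team working from the protocol would stop at about 56 consented, with the number randomised left open. Since the sample size has no power calculation behind it, the completer count is its only quantitative rationale, and both documents intend the data to help size the Phase II trial.

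**Working it through.** **Inputs**

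- Consented or recruited: about 56 (Protocol, General Study Design and Sample Size Justification).
- Completers: 48, which is 16 per arm in three arms (same sections).
- Non-completion: 15% (Sample Size Justification).
- Randomised: 48 (SAP, Statistical Plan).
- Fully evaluated: 48 (SAP, preliminary-efficacy text).

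**1. The protocol's own figure**

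- Number needed = completers / (1 − loss) = 48 / 0.85 = 56.5.
- In reverse, 56 × 0.85 = 47.6, which is 48 to the nearest person.
- The loss implied by going from 56 to 48 is 8 / 56 = 14.3%.

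The protocol's step is reproduced. The half-person difference is rounding.

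**2. The SAP's two figures**

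- Implied loss between randomised and fully evaluated = 1 − 48/48 = 0%.
- At the protocol's rate, 48 × 0.85 = 40.8 completers, and 40.8 / 3 = 13.6 per arm.
- Shortfall against 48: 48 − 40.8 = 7.2, about 7 participants.
- If each participant independently had a 15% chance of not completing, the chance that all 48 complete is 0.85^48 = 0.0004.

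**3. The 56 counted at consent**

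Let s be the proportion of consented participants who fail screening, and suppose the 15% starts at randomisation. Completers = 56 × (1 − s) × 0.85. The documents give no value for s, so these values are assumptions:

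| s (assumed) | Randomised | Completers |
|---|---|---|
| 0% | 56.0 | 47.6 |
| 5% | 53.2 | 45.2 |
| 10% | 50.4 | 42.8 |

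If the 15% is instead counted from consent and includes screen failures, completers are 47.6 whatever s is. So 48 is consistent with 56 consented under two conditions only: s is close to zero, or the 15% already covers it.

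**4. Can the two documents be reconciled as they stand?**

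One reading does it: 56 consent, 8 (14.3%) are lost before randomisation, and 48 are randomised. Nothing is then left for loss over the following 32 weeks. It also sits badly with Sample Size Justification, which discusses the loss in terms of interest in long-term treatment and staff training in keeping participants engaged, and sets expected retention against earlier cognitive interventions and PEERS groups. That describes loss during treatment.

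**The case against.** The best case on the other side has three parts.

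**The protocol's arithmetic is right.** A reader might infer that 56 consented cannot give 48 completers. The documents do not support this. At 15%, 56 gives 47.6, the protocol says approximately 56, and a shortfall appears only with a screen-failure rate that is nowhere stated. There are also reasons to expect few failures after consent. Under Recruitment, referring clinicians pre-screen, and staff go through the criteria with candidates before inviting them to consent. ASD diagnosis and IQ may be confirmed from records, and the capacity test applies only to 18-year-olds. This stands. What remains is that failures after consent are possible (the screening visit is paid whether or not the person proves eligible) and the plan does not say where they are counted.

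**The protocol does not say that 56 are randomised.** A reader might take 56 as the protocol's randomised number and see a flat 56-versus-48 conflict at randomisation. The protocol's words are consented and recruited, so the contradiction must be put more narrowly: 48 is the completers in the protocol, but both the randomised and the evaluated in the SAP.

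**Little depends on it.** A reader might infer lost power or lost precision on the primary outcomes. The number is explicitly practical, and the SAP concedes inadequate power. The primary outcomes are analysed in a CICADAS-users set defined by treatment received, not by completion, and programme completion is itself one of those outcomes. The mixed model also uses participants with incomplete data. This stands too, and it limits the importance of the point without removing the inconsistency.

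**Conclusion.** The inconsistency is real and narrow. The SAP's 48 randomised and 48 fully evaluated cannot both be expected under the protocol's 15%. With 48 randomised, the expected number of completers is about 41 (13 to 14 per arm), some 7 fewer than stated. The 56-to-48 step is correct if the 15% is counted from the 56, and is otherwise conditional on screen failures that the documents do not quantify.

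This rests on two assumptions: that the 15% is loss from the study, as the discussion of retention suggests, and that fully evaluated in the SAP means much the same as study completers in the protocol. Participants who stop using the programme may still be assessed if they have met the minimum sessions, so the evaluated number could exceed programme completers. It would still not be expected to equal the number randomised.

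The practical effect is modest. As a rough gauge, the 95% half-width for a standardised difference between two arms, 1.96 × √(2/n), goes from 0.69 at n = 16 to 0.75 at n = 13.6. That is a yardstick chosen here, since the SAP specifies only within-group effect sizes.

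**What to change.** State one chain, consented then randomised then completed, with the same numbers in both documents, and say from which point the 15% is counted and whether it includes screen failures. Then choose one:

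- **48 is the number randomised.** Restate the fully evaluated number in the SAP's power remark, and the completers in the protocol's General Study Design and Sample Size Justification, as about 41 (13 to 14 per arm). This costs wording only and needs no further enrolment.
- **48 is the number of completers.** Correct the SAP's Statistical Plan so that it no longer gives 48 as the number randomised, and apply the 56 at randomisation instead of at consent in the protocol. The edit is again wording, but any screen failures would then need consents beyond 56. The number needed is 56 / (1 − s): for example 59 at an assumed 5% or 63 at an assumed 10%, rounding up. The sponsor would have to supply its own rate.
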